## 5.4 Unscheduled Visits or Assessments

If the investigator determines that a subject should be monitored more frequently or with additional laboratory parameter assessments than indicated by the protocol-defined visit schedule, unscheduled visits or assessments are permitted. The laboratory assessments should be done by the central laboratory; however, if the results are needed immediately (eg, for AE management), they may be done by the local lab and the results forwarded to the management vendor for handling of local laboratory data unless a sample for central lab analysis is also collected. If study treatment is held, during the intervening time between the last dose and the time drug is restarted the study site should perform unscheduled visits (weekly or more frequently) as clinically indicated to monitor subject safety and appropriateness for re-treatment with study treatment. The requirement for or timing of unscheduled visits does not alter the requirement for or timing of scheduled visits.

#### 5.5 Procedure Details

This section describes the evaluations performed and items to be recorded or available on source documents.

# 5.5.1 Demographics, Medical and Cancer History

Demographics collected at screening will include date of birth (or age if date of birth is not allowed to be collected by local regulations), medical and cancer history (and current cancer status [ie; sites of disease]), surgical history, radiation therapy history, and systemic anti-cancer treatment history including names and administration dates of all investigational or approved TKIs.

# 5.5.2 Physical Examination

Physical examinations at screening will include height (screening visit only), weight, ECOG performance status, and an assessment of the following systems: skin, head, eyes, ears, nose, mouth and jaw, throat, respiratory system, cardiovascular system, gastrointestinal system, neurological condition, blood and lymphatic systems, and the musculoskeletal system. A symptom-directed physical examination including performance status will be conducted on W1D1 before first dose of study treatment. Any ongoing / intercurrent condition prior to first dose will be captured in source documents and on a CRF. New or worsening findings after first dose of study treatment are to be documented as adverse events.

# 5.5.3 Vital Signs

Vital signs including 5-minute sitting blood pressure, pulse, respiratory rate, and temperature will be assessed at screening, at all regularly scheduled visits, and at all unscheduled visits (if possible).

For blood pressure measurements, subjects should be seated quietly for at least 5 minutes in a chair, with feet on the floor, and arm supported at heart level. Caffeine, exercise, and smoking should be avoided for at least 30 minutes prior to measurement. An appropriately sized cuff (cuff bladder encircling at least 80 percent of the arm) should be used. At least two measurements should be made and the average systolic and diastolic values recorded (Joint National Committee on Prevention, Detection, Evaluation, and Treatment of High Blood Pressure 2004).

# 5.5.4 Electrocardiogram (ECG) Assessments

Standard 12-lead equipment will be used for all ECGs.

The Fridericia formula is depicted below for calculation of QTcF.

$$QTcF = \frac{QT}{RR^{1/3}}$$

QT = measured QT interval in milliseconds; RR = measured R to R interval (which can be derived from the heart rate [HR] as 60/HR)

ECGs to establish eligibility must be done within 28 days prior to randomization (Appendix A). To confirm suitability for treatment after randomization, ECGs must be repeated on W1D1 prior to administering the first dose of study treatment unless screening tests were performed within 14 days prior to W1D1.

At screening, if the initial QTcF is > 500 ms, a total of 3 ECGs each separated by at least 3 minutes should be performed. If the average of these three consecutive results for QTcF is  $\leq 500$  ms, the subject meets eligibility in this regard.

During the study, single ECG assessments will be performed as indicated in Appendix A. If cardiac abnormalities are detected or suspected, two additional ECGs must be performed at intervals at least 3 minutes apart in order to confirm the finding. If at any time while on study there is an increase in average QTcF > 500 ms or an increase >60 ms above baseline, study treatment must be immediately interrupted and instructions in Section 6.5.2.10 for continued monitoring of QTc must be followed.

Abnormalities in the ECG that lead to a change in subject management (eg, dose reduced or withheld, treatment discontinued, requiring additional medication or monitoring), or that result in clinical symptoms are considered clinically significant for the purposes of this study and should be reported as AEs by the investigator. If values meet criteria defining them as serious, they must be reported as SAEs (Section 8.2).

# 5.5.5 Laboratory Assessments

Laboratory analytes that will be measured for this study are listed in Table 5-1. The schedule for laboratory assessments is provided in Appendix A.

Hematology, serum chemistry, coagulation, UPCR (and components), and thyroid function tests are to be performed by a central laboratory, including unscheduled visits (if possible). Central laboratory results will be provided to the investigator. Local laboratory assessments for these panels are permitted for these assessments if the results are required by the investigator in a rapid

timeframe (such as for monitoring of AEs), but may not be used to establish eligibility. In rare, exceptional circumstances and with approval of the Sponsor, local laboratory result may be allowed for the purpose of determining eligibility in the event that the result of an individual test performed at the central laboratory is unavailable. Local laboratory results for these panels must be forwarded to the study local laboratory management vendor if performed in lieu of the central laboratory assessment at any scheduled or unscheduled visit.

Routine (dipstick) urinalysis, microscopic urine examination, and serum pregnancy tests are to be done by local laboratory. Results or status from these tests will be recorded on CRFs and will not be submitted to the study local laboratory management vendor.

Tests for 24-hour urine protein tests, if performed to determine eligibility or at any scheduled or unscheduled visit, are to be done by local laboratory and the lab results forwarded to the study local laboratory management vendor.

Laboratory tests to establish eligibility must be done within 28 days prior to randomization (Appendix A) except for serum pregnancy tests which must be done within 7 days prior to randomization. If the investigator suspects the subject is clinically deteriorating during the screening period, additional unscheduled laboratory tests should be performed by the local laboratory before randomization to confirm that the subject remains suitable for study treatment and amenable to study participation commensurate with the goals of the clinical trial.

To confirm suitability for treatment after randomization, laboratory tests (except for pregnancy test) must be repeated on W1D1 prior to administering the first dose of treatment unless the screening tests were performed within 14 days prior to W1D1 or if the subject has experienced a change in clinical status. A serum pregnancy test for females of child-bearing potential must be repeated before dosing on W1D1 unless the screening test was performed within 7 days prior to W1D1.

Once Investigators have been notified by the Sponsor about the start of the Treatment Period - Maintenance Phase (see Section 5.2.1), central laboratory testing for this study will discontinue, and subjects remaining on study treatment will undergo local laboratory tests per SOC.

**Table 5-1:** Laboratory Panels

## **Central Laboratory**

If performed by local laboratory in lieu of central lab assessment, submit results to study local laboratory management vendor

## Hematology

- White blood cell count (WBC) with differential (neutrophils [absolute neutrophil count; ANC], basophils, eosinophils, lymphocytes, monocytes)
- hematocrit
- platelet count
- red blood cell count
- hemoglobin
- reticulocytes

# Coagulation

- Prothrombin time/international normalized ratio (PT/INR)
- Partial thromboplastin time (PTT)

#### Other Parameters

- Calcitonin (CTN)
- Carcinoembryonic Antigen (CEA)

## **Serum chemistry**

- Albumin
- total alkaline phosphatase
- amylase
- alanine aminotransferase (ALT)
- aspartate aminotransferase (AST)
- blood urea nitrogen (BUN)
- calcium (corrected)
- bicarbonate
- chloride
- creatinine
- γ-glutamyltranspeptidase (GGT)
- glucose
- lactate dehydrogenase (LDH)
- lipase
- magnesium
- phosphorus
- potassium
- sodium
- total bilirubin (conjugated and unconjugated if clinically indicated)
- total protein

#### **Urine chemistry**

- Protein (spot urine; fully quantitative)
- Creatinine (spot urine; fully quantitative)
- Urine protein/creatinine ratio (UPCR; spot urine) a

#### **Thyroid function**

- Thyroid stimulating hormone (TSH)
- Free T4

## **Local Laboratory**

Submit only 24-hour urine protein test results to study local laboratory management vendor

# Urinalysis (Dipstick or Routine)

- pH
- specific gravity
- ketones
- protein
- glucose
- nitrite
- urobilinogen
- leukocyte esterase
- blood

#### 24-Hour Urine

• 24-hour urine proteina

• Perform at the discretion of the investigator based on results or routine urinalysis or as clinically indicated

Microscopic Urine Examination

# Pregnancy (serum)

• β-human chorionic gonadotropin (β-HCG)

When UPCR exceeds 1, a repeat UPCR or a 24 hour urine protein should be performed to confirm the result (see Table 6-10)

Clinically significant laboratory abnormalities should be reported as AEs by the Investigator. In general, laboratory abnormalities that lead to a change in subject management (eg, dose withheld or reduced, treatment discontinued; requirement for additional medication or monitoring) are considered to be clinically significant. If laboratory values constitute part of an event that meets criteria defining it as serious, the event (and associated laboratory values) must be reported as a serious AE (SAE) (see Section 8.2).

In cases of discordance on AE grading between duplicate local and central labs, the lab abnormality with the higher grade should be referenced for AE reporting purposes.

#### **5.5.6** Disease Assessments

#### **5.5.6.1** General

Radiographic tumor assessments should be performed according to the schedule in Appendix A. This schedule is to continue irrespective of whether study treatment is given, interrupted, reduced or discontinued, through the later of:

- 12 weeks after radiographic progression per RECIST 1.1 as determined by the investigator (ie, one additional assessment after investigator-determined radiographic progression), or
- The date of the decision to discontinue study treatment (eg, for subjects treated beyond radiographic progression per RECIST 1.1)

However, these assessments are to be discontinued if subsequent systemic anti-cancer therapy, radiation therapy, or surgery affecting tumor lesion(s) is initiated prior to meeting these above criteria.

Tumor response will be assessed using RECIST 1.1 (Appendix D). All known lesions will be assessed. All site assessments of radiographic images will be performed by a radiologist.

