## 7.1.2 Prohibited or Restricted Therapies

The following therapies are prohibited while the subject is on study treatment:

- any investigational agent or investigational medical device
- any drug or herbal product used specifically for the treatment of MTC
- therapeutic doses of oral anticoagulants (eg, warfarin or warfarin-related agents, thrombin or FXa inhibitors, antiplatelet agents such as clopidogrel)
- any other systemic anti-cancer treatment (eg, chemotherapy, immunotherapy, radionuclides)

The following therapies should be avoided while the subject is on study treatment

- Local anti-cancer treatment including palliative radiation, ablation, embolization, or surgery with impact on tumor lesions should not be performed until radiographic tumor assessments and study treatment have been discontinued per protocol defined criteria. If clinically unavoidable, treatment should be held prior to the intervention and the investigator should discuss with the sponsor to assess for any safety concerns (ie, length of treatment interruption). Subjects who have such an intervention may be considered not evaluable (and may be assigned a censoring or progression date) for certain efficacy endpoints. If such therapies are used to retard the progression of a subject's underlying disease, the subject will discontinue study treatment (as this constitutes a protocoldefined endpoint).
- Erythropoietic-stimulating agents (eg, epoetin alfa and darbepoetin alfa) should not be used based on a report of increased risk of tumor recurrence/progression associated with erythropoietin (Wright 2007).
- Chronic co-administration cabozantinib with strong inducers of the CYP3A4 family (eg, dexamethasone, phenytoin, carbamazepine, rifampin, rifabutin, rifapentin, phenobarbital, and St. John's Wort) may significantly decrease cabozantinib concentrations and should be avoided. Selection of alternate concomitant medications with no or minimal CYP3A4 enzyme induction potential is recommended.
- Caution must be used when discontinuing treatment with a strong CYP3A4 inducer in a subject who has been concurrently receiving a stable dose of cabozantinib, as this could significantly increase the exposure to cabozantinib

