# **9.2.1.2 Analysis**

The primary efficacy analysis of PFS will include all subjects in the ITT population and will evaluate whether PFS in subjects in the 60 mg cabozantinib arm is non-inferior to subjects in the 140 mg cabozantinib arm. It will include radiographic progression (rPD) events per RECIST 1.1 as determined by the IRC and deaths. The primary efficacy analysis is event based and will be conducted when at least 150 PFS events have been observed.

The following censoring rules will be applied:

- Subjects receiving subsequent anti-cancer therapy (other than palliative bone radiation) before rPD per IRC will be censored at the date of their most recent post-randomization adequate tumor assessment prior to receipt of such therapy
- Subjects who miss two or more scheduled adequate tumor assessments before rPD or death will be censored at the date of their most recent post-randomization adequate tumor assessment prior to the missed assessments
- Subjects who have not progressed or expired as of the date of the analysis data cutoff will
  be censored at the date of their most recent post-randomization adequate tumor
  assessment prior to the data cutoff date
- Censored subjects without an appropriate post-randomization adequate tumor assessment will be censored at the date of randomization

Radiographic assessments are to continue if treatment is discontinued for reasons other than rPD, per the ITT principle such subjects will not necessarily be censored.

Sensitivity analyses with alternative definitions and censoring rules will be defined in the SAP to demonstrate the robustness of the treatment effect and explore the impact of potentially informative censoring.

The median duration of PFS and its associated confidence interval (CI) will be estimated using the Kaplan-Meier product-limit method. The hazard ratio (HR) and the associated 95% CI will be estimated using a Cox proportional- hazards model with treatment group as the independent variable and stratified by the factors that were used for randomization.

Non-inferiority will be concluded if the upper 95% CI for the HR is less than the non-inferiority margin of 1.58.

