2.6 Radiographic Tumor Assessment

Radiographic tumor measurements will be made at screening, 12 weeks after randomization, and every 12 weeks thereafter. This schedule is to continue irrespective of whether study treatment is given, interrupted, reduced or discontinued. Tumor assessments will continue (and scans submitted to the IRC) through the later of:

- 12 weeks after radiographic progression per RECIST 1.1 as determined by the investigator (i.e., one additional assessment after investigator-determined radiographic progression), or
- The date of the decision to discontinue study treatment (eg, for subjects treated beyond radiographic progression per RECIST 1.1)

However, these assessments are to be discontinued if subsequent systemic anti-cancer therapy, radiation therapy, or surgery affecting tumor lesion(s) is initiated prior to meeting these above criteria.

An IRC will evaluate all blinded scans per RECIST 1.1 for disease progression and objective response for the purpose of evaluating primary and secondary study endpoints. Subject management and treatment decisions will be based upon investigator evaluations of the scans. The roles, responsibilities, and details of the processes followed by the IRC are provided in the IRC charter.

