7.1.3 Primary Analysis

The primary efficacy analysis of PFS will include all subjects in the ITT population and will evaluate whether PFS for subjects in the 60 mg cabozantinib arm is non-inferior to PFS in subjects in the 140 mg cabozantinib arm. The primary efficacy analysis is event based and will be conducted when at least 150 PFS events have been observed.

The recorded date of radiographic progression is the date of the tumor assessment visit at which progression is declared per IRC per RECIST 1.1. If multiple scan dates are associated with a tumor assessment visit, the earliest assessment date within the set will be chosen as the progression date.

Only adequate tumor assessments (ATAs) will be considered in the determination of radiographic progression and censoring dates. For the purpose of this study, ATA is defined as one that results in a time point assignment of: response (complete or partial), stable disease/(non-

CR, non-PD), or progression. For PFS, ATA is based on soft tissue evaluation by CT/MRI.

Single missing or inadequate scheduled tumor assessments will be ignored. No values will be imputed.

The censoring rules shown in Table 3 will be applied to the primary and sensitivity analyses of PFS.

Table 3: Censoring Rules for Analyses of Progression Free Survival

Туре		PFS-A1		PFS-B1	
Analysis	Primary		Primary		
Radiographic PD per		IRC	Investigator		
Population		ITT		ITT	
Condition	Outcome	Date of Outcome	Outcome	Date of Outcome	
No post-baseline ATA	Censored	Date of randomization	Censored	Date of randomization	
Death	Event	Date of death	Event	Date of death	
Radiographic soft-tissue PD	Event	Date of PD	Event	Date of PD	
Clinical deterioration	NA	NA	NA	NA	
Any systemic non-protocol anti- cancer therapy (NPACT) received on or after randomization date	Censored	Date of last ATA on or prior to initiation of therapy	Censored	Date of last ATA on or prior to initiation of therapy	
Radiation (other than to bone)	Censored	Date of last ATA on or prior to radiation	Censored	Date of last ATA on or prior to radiation	
Surgery impacting soft tissue lesions	Censored	Date of last ATA on or prior to surgery	Censored	Date of last ATA on or prior to surgery	
≥ 2 consecutive missing scheduled ATA immediately prior to rPD or death	Censored	Date of last ATA prior to the missing assessments.	Censored	Date of last ATA prior to the missing assessments.	

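### Tumor scans stop after any radiation, including the palliative bone radiation that the PFS rules exempt from censoring, so the exemption cannot work

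*Protocol*

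**What the plan says.** Three sets of rules apply to a subject who receives palliative radiation to a bone metastasis before IRC progression.

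- **Imaging.** Protocol 5.5.6.1 sets 12-weekly scans regardless of dosing status, then adds: "However, these assessments are to be discontinued if subsequent systemic anti-cancer therapy, radiation therapy, or surgery affecting tumor lesion(s) is initiated". The same clause stands in the synopsis (Study Design, Tumor Assessments), Protocol 3.3 and 5.2, the Appendix A table and footnote, and SAP 2.4 and 2.6 ("radiation therapy, or surgery affecting tumor lesion(s) is initiated prior to meeting these above"). None of these places excepts bone.
- **PFS censoring.** Protocol 9.2.1.2 states: "Subjects receiving subsequent anti-cancer therapy (other than palliative bone radiation) before rPD per IRC will be censored". SAP Table 3 (section 7.1.3) has a censoring row for radiation restricted by "Radiation (other than to bone" and another for "Surgery impacting soft tissue lesions". Bone radiation is neither a censoring condition nor an event in any column.
- **Local therapy on study.** Protocol 7.1.2 discourages palliative radiation until scans and study drug have ended, but continues: "If clinically unavoidable, treatment should be held prior to the intervention and the investigator should discuss with the sponsor". Discontinuation is tied to purpose: "If such therapies are used to retard the progression of a subject's underlying disease, the subject will discontinue study treatment". The list in Protocol 3.5.3 ties it to the same purpose. Protocol 7.1.2 also lets such subjects be treated as not evaluable, or be given either a censoring date or a progression date.

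SAP Table 3 defines two or more missed assessments as more than 178 days without an evaluation.

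**The concern.** Exempting a therapy from censoring has a purpose only if progression can still be observed after it. Here the analysis rule keeps the subject at risk for IRC progression while the data-collection rule ends the scans. The subject then falls to one of two rows of Table 3: the residual row (censored at the last adequate assessment) or, if death comes more than 178 days later, the missed-assessment row (censored at the same date). Only a death within 178 days still counts.

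Two things are at stake. The first is events, in a trial that already provides for an increase to 250 subjects because censoring may keep it from reaching 150. The second is the nature of the censoring. Subjects who need bone radiation may be close to progression, so losing their scans may be informative. If that happened more often at 60 mg, the hazard ratio would move toward 1, which in a non-inferiority trial favours the claim.

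**Working it through.** **Reading the rules in sequence.** Take a subject on blinded drug with no IRC progression and unavoidable palliative radiation to bone.
1. Protocol 7.1.2 and 3.5.3: drug is held but need not be stopped, because the purpose is not to retard progression.
2. Protocol 9.2.1.2 and SAP Table 3: the radiation does not censor.
3. Protocol 5.5.6.1 and SAP 2.6: scheduled scans end.
4. SAP Table 3: with no later assessment, the subject is censored at the last one, unless death occurs within 178 days.

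The sensitivity analyses do not repair this. PFS-A2 turns only non-bone radiation into an event. PFS-A3 changes only gaps that end in progression or death. A living, unscanned subject is censored at the last assessment in every IRC analysis.

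**The plan's own figures.** The margin is exp[ln(1/0.40)/2] = 1.5811. With one-sided alpha 0.025, 80% power and true HR 1, events = 4(1.960 + 0.842)²/(ln 1.5811)² = 149.6, so 150, as stated. Power at 150 events is 80.1%.

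For timing, Protocol synopsis (Sample Size) gives 188 subjects at 5 per month, so accrual A = 37.6 months, and a median PFS of 11.2 months, so λ = ln 2/11.2 = 0.0619 per month. Take both arms exponential with no dropout, and let p be the share of subjects who eventually lose scans to bone radiation before a PFS event, at a constant competing rate. With L = λ/(1 − p), expected events at month T are

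E = 188(1 − p){1 − [exp(−L(T − A)) − exp(−LT)]/(L·A)}.

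At p = 0 and T = 48: 188{1 − (0.5254 − 0.0513)/2.327} = 149.7, against the plan's 150 at 48 months.

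**Event loss.** The documents give no rate of palliative bone radiation, so p is assumed. Power at that cutoff is Φ(½√E · ln 1.5811 − 1.96).

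| Assumed p | Events at 48 months | Power at that cutoff | Month when 150 is reached |
|---|---|---|---|
| 0 | 149.7 | 80.0% | 48.1 |
| 2% | 147.8 | 79.5% | 49.0 |
| 5% | 144.8 | 78.7% | 50.6 |
| 10% | 139.6 | 77.2% | 54.3 |
| 15% | 134.2 | 75.6% | 61.2 |

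This slightly overstates the loss, because deaths within 178 days would still count.

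**Bias.** Let a and b be the fractions of progressions lost at 140 mg and 60 mg. If each lost subject would have progressed at the moment of censoring (fully informative), the observed HR at a true HR of 1.58 is 1.58(1 − b)/(1 − a). With a = 5% and b = 10% (assumed), it is 1.58 × 0.90/0.95 = 1.497. With SE = 2/√150 = 0.163, the chance that the upper limit falls below 1.58 is

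Φ[(ln 1.58 − 1.96 × 0.163 − ln 1.497)/0.163] = Φ(−1.63) = 5.2%, against 2.5% with no loss.

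I checked this by simulating 20,000 trials of 94 per arm, analysed at 150 events. Fully informative loss gave 5.3% with a mean HR of 1.50. The same unequal loss, but independent of progression, gave 2.5% with a mean HR of 1.58. If the larger loss fell on 140 mg instead (a = 10%, b = 5%), the formula gives HR 1.668 and 1.1%, so the bias runs the other way.

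**The case against.** The strongest reply is that the case is rare and discouraged. Protocol 7.1.2 asks that palliative radiation wait until scans and study drug have ended, requires discussion with the sponsor, and says how such subjects may be dated for efficacy. That stands as to frequency. It does not resolve the conflict, because a discretionary choice of censoring or progression date agrees with neither 9.2.1.2 nor Table 3. Nor is the case remote: exclusion criterion 5 has its own washout for radiation to bone metastases.

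The words about affecting tumor lesions might also be read to limit the radiation covered. A bone metastasis is a tumor lesion, however. Protocol 5.5.6.3 follows bone lesions by CT or MRI, and Appendix D lets some of them be measurable. Table 3 bases adequacy for PFS on soft tissue, which bone radiation does not of itself prevent from being assessed.

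Several stronger readings are tempting and are not supported:
- *That the PFS rules forbid ending follow-up after bone radiation.* They only exempt it from censoring.
- *That Protocol 9.2.1.2 also exempts surgery.* It does not mention surgery. Bone-only surgery is left uncensored by SAP Table 3 alone. For systemic therapy, non-bone radiation and surgery to soft tissue lesions, the stopping rule and Table 3 agree.
- *That 188 − 150 = 38 is the whole allowance and each irradiated subject uses one place.* The plan can go to 250, and some of these subjects would have had no event by the cutoff anyway. At 5% the loss is about 5 events, not the 9 that 5% of 188 suggests.
- *That false non-inferiority should be expected to rise.* It rises only if loss is informative and also heavier at 60 mg.
- *That investigators would have no imaging to guide treatment.* Protocol 5.4 permits unscheduled assessments. What ends is the required schedule.

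**Conclusion.** The point holds, confined to palliative bone radiation. The imaging rule, the censoring rule and Protocol 7.1.2 give three different answers for the same subject, and no section reconciles them. Followed as written, they make scheduled IRC progression assessment unavailable in subjects whom the endpoint definition keeps at risk.

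The size is modest and rests on assumed rates. At 5% or 10% affected, about 5 or 10 events are missing at 48 months. In an event-driven analysis this costs roughly 2.5 or 6 months, or use of the increase to 250, rather than final power. The rise in false non-inferiority from 2.5% to about 5% is a worst-case illustration for its assumed loss rates, because it takes every lost subject to be on the point of progression. It is not an expected value. It should be corrected because the primary endpoint depends on it and the correction is cheap.

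**What to change.** - In Protocol 5.5.6.1, the synopsis (Study Design, Tumor Assessments), 3.3, 5.2, the Appendix A table and footnote, and SAP 2.4 and 2.6, except palliative radiation to bone from the scan-stopping clause. State that the 12-weekly scans and IRC submission then continue under the usual criteria.
- Reconcile the efficacy-dating sentence in Protocol 7.1.2, and its statement on the order of scans and local therapy, with 9.2.1.2 and Table 3.
- Add a line to Table 3 saying how subjects with bone radiation are handled, and align the surgery wording of the stopping clause with its row on soft tissue lesions.
- Tabulate palliative bone radiation before IRC progression by arm, so that any imbalance can be seen. SAP 6.9 already summarizes post-randomization radiation.

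The cost is wording changes in both documents and a few scans, already on the schedule, in the affected subjects.
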